 - a. Remind her of time for scheduled call
 - b. Remind her that the videos need to be created:
 - i. At time when your baby has been recently fed, is not sleepy and is feeling well
 - ii. Away from other people so that the interaction will not be interrupted by other people in the home;
 - iii. Away from sources of noises that could be picked up on the camera's microphone (like a noisy kitchen, television, or street)

- c. Remind her, if applicable, of the fun activity for her older children, which they are going to get set up before the call with you
- d. Confirm that she has all the project materials that were sent to her & that her phone will be charged to at least 50% for the call. She will want to have headphones to use for the surveys unless it is just her and the baby in the home.

Pre-Assessment Call: Videos & Questionnaires [Assigned Coach]

(Split into 2 calls, 1 hour each; schedule 2 days as close together as possible)

1. Prior to getting on call
 - a. Gather needed paperwork (or go to electronic versions on Dropbox -> MomAndBabyNetNIHR01 -> Assessment -> Assessment Protocols & Forms -> Remote Assessments
 - i. ASRI
 - ii. Data checklist
 - iii. PDFs of surveys
 - iv. If mom is using a laptop/tablet to complete the surveys, have an email prepped with the link to send her. Do not send the day before.
2. Start Zoom call and greet mom as you normally would.
3. Zoom & iPhone orientation
 - a. Make sure mom is familiar with Zoom and troubleshoot if she has any issues with audio, video, etc.
 - b. Ask mom if she's ever used an iPhone before.
 - i. If not, give her a brief tutorial (turning off and on; answering phone; sending texts; Safari browsing; opening and closing apps; taking screenshots). Reference handbook section that covers this.
 - ii. Show mom all of the contacts that you added to her phone and explain the method for entering them (e.g., DR Smith Pediatrician; MED Poison Control). Reference handbook section that covers this.
 - iii. Show mom how to add numbers to Favorites (coach has already been added to favorites).
4. Review what you will be doing for the assessment part of the project

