 6. To mom: *You can begin now.* Coach – mute your microphone to mute your own background noise.
 7. After 5:30 minutes, stop recording on Zoom, unmute yourself, and say *Ok, the second video is finished.*

- e. Reset Zoom

- i. *Great job on the videos! Now we can continue to the surveys. So we don't run out of time, I am going to end this call and we are going to get right back on this same Zoom to continue.*
- ii. End Zoom call then start again immediately.
- iii. Ask mom if she needs to take care of any needs for the baby or if she is able to put the baby down or give to another adult so she can focus on the surveys.

6. Questionnaires

- a. Pre Assessment Questionnaire Part 1 (labeled as part 2 in Qualtrics: T1_part2)
 - i. *Now we will begin the questionnaires. They are split into two parts, so we don't have to complete both today. Each part will take 30-40 minutes to complete. We can start Part 1 and see how far we get. If we need to, we can complete the rest of the survey on our next scheduled call.*
 - ii. *I am now sending you a link to the first survey we will complete. Please let me know when you have received it and you can go ahead and click on it.*
 - iii. Send link to T1_Part 2 survey to mom
 - 1. Link: (see links document)
 - 2. If mom is doing surveys on their phone, text survey link to mom's project phone
 - 3. If mom is using laptop, email survey link
 - 4. If mom is restarting a partially finished survey, see steps below to get link to that survey and start where she left off
 - iv. Coach will have PDF of survey open to look at (printed or on computer). If mom needs to stop before reaching the end of this survey, make a note on the PDF of where she ended.
 - v. Set up surveys
 - 1. If mom is using their project phone: *When you click on the link, we will stay on Zoom. Even though we won't be looking right at each other through video, I will walk you through everything.*
 - 2. If mom is using own laptop/table: *If you want to set your phone up somewhere during these surveys, we will not necessarily need to see each other, but I will be walking you through each section of the survey.*
 - vi. Coach will instruct mom how to fill out the first page of info: ID #, mom initials, assessor name, date (mm/dd/yyyy)
 - vii. Read instructions for each section
 - 1. Coach will read through introductory instructions and instructions for first section.

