- ix. Make sure mom clicks final 'submit' button to record answers. She will see a full copy of the entire survey.
 1. *Great job - you have finished the surveys! Please give me a few minutes to make sure everything submitted ok.*
- x. Check survey in Qualtrics
 1. Coach will log into Qualtrics (sign in page link)
 2. Look for T1_Part1 survey
 3. Click on 3 dots to the right of that survey and click 'Data & Analysis'
 4. Look for mom's ID # and info for that survey to confirm submission; if not there yet, wait a minute and refresh
- xi. Record embedded data on ASRI
 1. Check ATQ self harm item ('ATQ6' column in Qualtrics)
 - a. If response of 3, 4, or 5 – check box

- b. Tell mom: *The only responses I can see are items related to your safety and I wanted to follow up on this item.*
- c. Follow decision tree to address potential safety concern with mom
- d. Check appropriate box under 'Self Harm' after completing decision tree discussion
- c. *Great job – you finished the surveys! Now we just have some final information to go over together.*
- d. Unfinished surveys
 - i. If a mom needs to stop either Part 1 or Part 2 of the survey before she gets to the end, that is ok.
 - ii. Tell mom: *We can definitely stop and pick back up tomorrow. Make sure you finish the page you are on and click to the next page so it saves. Then you can close the browser/window.*
 - iii. Wrap up the call with mom and confirm the time you will be meeting tomorrow via Zoom.
 - iv. Make a note of where mom ended (ideally mark the page if you have the PDF printed)
 - v. About 4 hours after you end the call, check Qualtrics to make sure the incomplete survey submitted.
 - 1. Log into Qualtrics
 - 2. Find survey that was partially completed
 - 3. Click on 3 dots to the right of that survey and click 'Data & Analysis'
 - 4. Look for mom's ID # and info for that survey to confirm submission; if not there yet, wait a little while and refresh to check again
 - vi. Restart survey the next day
 - 1. Before starting call again with the mom, log into Qualtrics
 - 2. Find survey that was partially completed
 - 3. Click on 3 dots to the right of that survey and click 'Data & Analysis'
 - 4. Find mom's partially completed survey (by ID and date)
 - 5. On that line, to the very right, click the arrow under the 'Actions' column
 - 6. Click 'Retake Response' (do NOT click 'Retake as New Response')
 - 7. A box will pop up with a link – this is the link you will send to the mom

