 - 8. When she clicks on the link, the survey will open to the first page (ID, mom initials, etc.) but should be completed already. Instruct her to click through until she reaches the page where she left off.
 - 9. Review the instructions again for the section she is on.
 - 10. Continue as usual through the rest of the survey.

Schedule App Training Visit

1. Explain app training visit
 - a. *On our next call, we will get familiar with the Mom & Baby Net app and start the first session together.*

2. Ask mom some questions to determine the best time and way to complete the call remotely
 - a. Discuss devices to use for this call
 - i. If mom used a personal phone or laptop for the pre assessment calls, tell her she might want to do the same for the next call. She can connect to Zoom through her personal device then use the project phone to learn the app.
 - ii. If mom does not have another device to use, ensure her that is perfectly fine, and they will be able to do everything through the project iPhone
 - b. Ask questions to help mom determine when would be the best time to do the call. Some moms may know exactly when a good time is while others may need to think through some of these questions to figure it out. The purpose of these is to prime mothers for a successful video capture call.
 - i. *If possible, we want to schedule the call at a time when your baby is napping or resting or can be with another adult so you can focus on the call and follow along in the app.*
 - ii. If you know there are other children in the home: *How did the activity for your older children work during these pre assessment calls? What was it?* If it was appropriate, find out the details so you can encourage it again for the next call. If it is not appropriate or feasible, then help her think of something that is (i.e. watching an appropriate movie/show, playing a game). *When did they do that? Where? How long?* If the mother identifies something realistic and doable, encourage her to do that and have her set the specific reminder on her phone to get the other kids set up doing that activity 15 minutes BEFORE your scheduled call.
3. After working through these questions, schedule a 1.5 hour call to complete the App Training (may not take that long but have it scheduled in case it does)
4. Enter scheduled day/time into Access database.

Immediately After Pre-Assessment Call(s)

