 17. After 5:30 minutes, stop recording on Zoom, unmute yourself, and say *Ok, the second video is finished.*
- e. Reset Zoom
 - i. *Great job on the videos! Now we can continue to the surveys. So we don't run out of time, I am going to end this call and we are going to get right back on this same Zoom to continue.*
 - ii. End Zoom call then start again immediately.
 - iii. Ask mom if she needs to take care of any needs for the baby or if she is able to put the baby down or give to another adult so she can focus on the surveys.

5. Questionnaires
 - a. Post Assessment Questionnaire Part 1 (labeled as part 2 in Qualtrics: T2_part2)
 - i. *Now we will begin the questionnaires. They are split into two parts, so we don't have to complete both today. They are very similar to the questionnaires you completed at your very first home visit. Each part will take 30-40 minutes to*

complete. We can start Part 1 and see how far we get. If we need to, we can complete the rest of the survey on our next scheduled call.

- ii. I am now sending you a link to the first survey we will complete. Please let me know when you have received it and you can go ahead and click on it.*
- iii. Send link to T2_Part 2 survey to mom
 1. Link: (see links document)
 2. If mom is doing surveys on their phone, text survey link to mom's project phone
 3. If mom is using laptop, email survey link
 4. If mom is restarting a partially finished survey, see steps below to get link to that survey and start where she left off
- iv. Coach will have PDF of survey open to look at (printed or on computer). If mom needs to stop before reaching the end of this survey, make a note on the PDF of where she ended.
- v. Set up surveys
 1. If mom is using their project phone: *When you click on the link, we will stay on Zoom. Even though we won't be looking right at each other through video, I will walk you through everything.*
 2. If mom is using own laptop/table: *If you want to set your phone up somewhere during these surveys, we will not necessarily need to see each other, but I will be walking you through each section of the survey.*
- vi. Coach will instruct mom how to fill out the first page of info: ID #, mom initials, assessor name, date (mm/dd/yyyy)
- vii. Read instructions for each section
 1. Coach will read through introductory instructions and instructions for first section.

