 - iv. Make a note of where mom ended (ideally mark the page if you have the PDF printed)
 - v. About 4 hours after you end the call, check Qualtrics to make sure the incomplete survey submitted.
 1. Log into Qualtrics
 2. Find survey that was partially completed
 3. Click on 3 dots to the right of that survey and click 'Data & Analysis'
 4. Look for mom's ID # and info for that survey to confirm submission; if not there yet, wait a little while and refresh to check again
 - vi. Restart survey the next day
 1. Before starting call again with the mom, log into Qualtrics
 2. Find survey that was partially completed
 3. Click on 3 dots to the right of that survey and click 'Data & Analysis'
 4. Find mom's partially completed survey (by ID and date)
 5. On that line, to the very right, click the arrow under the 'Actions' column
 6. Click 'Retake Response' (do NOT click 'Retake as New Response')
 7. A box will pop up with a link – this is the link you will send to the mom

8. When she clicks on the link, the survey will open to the first page (ID, mom initials, etc.) but should be completed already. Instruct her to click through until she reaches the page where she left off.
9. Review the instructions again for the section she is on.
10. Continue as usual through the rest of the survey.

6. End of program information

- a. Follow-ups and video release
 - i. *The last thing we ask moms to complete is one follow-up. We will not have to see you for these. 6 months after today, you will get an email that has a link to a 5-10 minute survey. If you do not complete the survey on your own, we will follow up via phone to remind you and you can do it over the phone if you want. Do you have any questions about the follow up? I will also send you the date for your follow up through Coach Talk.*
 - ii. *I am sending you a link now to a form. Please let me know when you get it and I will go through it with you.*
 1. Send mom link the same way survey links were sent
 2. bit.ly/MBNpostInfo
 - iii. *Once mom has form open: First, we need the best email address to reach you. This is where the follow-up email will come 1 month from today.*
 - iv. *Next, please put the best phone number, other than the project phone number, to reach you. Then you can click to the next page.*

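### In the remote procedures, no step directs a read of PHQ9 #9 or ATQ #6 in an unfinished survey part until that part is completed, normally the next day

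*Protocol*

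**What the plan says.** The point is confined to Protocol Part VI. Each remote assessment has two survey parts, completed while the coach is on a video call. The part given first holds the PHQ9 and the part given second holds the ATQ (Qualtrics labels them the other way round).

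Each part has one directed read of its self-harm item. In the Pre-Assessment Call, PHQ9 #9 is read at item 6a step xii, and ATQ #6 at item 6b step xi. In the Post Assessment Call, both reads are at step xii, of items 5a and 5b. A PHQ9 #9 response of 1 to 3, or an ATQ #6 response of 3 to 5, leads to the decision tree in Part IV.

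The script expects that the first part may not be finished in one call: "We can start Part 1 and see how far we get. If we need to, we can complete the rest of the survey". Item 6d, Unfinished surveys, then applies. The mother is told: "Make sure you finish the page you are on and click to the next page so it saves". The coach notes where she stopped and later returns to the record: "About 4 hours after you end the call, check Qualtrics to make sure the incomplete survey submitted". Next comes "Restart survey the next day", where the coach logs in again to obtain a link. On the call, the direction is "Instruct her to click through until she reaches the page where she left off", after which the part carries on as normal. Item 5d of the Post Assessment Call repeats these steps.

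**The concern.** These mothers entered the trial because they screened positive for depression. The Part IV decision tree starts when a mother reports thoughts of death or suicide, and it names ATQ #6 and PHQ9 #9 as ways of reporting them. It does not wait for a finished questionnaire. A mother who endorses an item and then stops has arguably met that trigger, yet a coach who follows the unfinished-survey steps exactly has no instruction to look.

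The stake is participant safety: a self-harm follow-up that starts about a day later than it might, or that nothing in the manual starts if she drops out between calls. Randomization, the outcomes and the SAP analyses are not affected.

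**Working it through.** The plan gives no figure to reproduce. The check is a trace of the step order, followed by simple timing.

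**1. Order of steps for a completed part**

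| Part | Final submit | Coach confirms in Qualtrics | Item read |
|---|---|---|---|
| Pre, PHQ9 (6a) | x | xi | xii |
| Pre, ATQ (6b) | ix | x | xi |
| Post, PHQ9 (5a) | x | xi | xii |
| Post, ATQ (5b) | x | xi | xii |

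In all four, the read follows the mother's own final submit.

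**2. Staff contact with an unfinished part (6d and 5d)**

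- At about 4 hours: find her ID and see that the record is stored. Neither item is named.
- Before the restart call: find the record and copy the link. Neither item is named.
- On the restart call: she finishes, so the steps in the table apply and the item is read.
- If she does not resume: no step is given.

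**3. Other text that might close the gap**

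- The split-visit note (Part II, After Home Visit) asks for a risk form for each visit, but only once there is a concern about harm. It belongs to the in-home procedure.
- The risk form (ASRI) has boxes for both items, and the Data Checklist has a line on following up endorsed safety questions. Both presuppose that someone has read the answers.
- The decision tree also covers spontaneous disclosure, which does not depend on the record.

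None of these sends a coach to a partial record.

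**4. Timing**

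Assume the restart call is at the same hour the next day.

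- First directed read now: about 24 h after the stop.
- Read at the existing check, if the items are visible: about 4 h.
- Gain: 24 − 4 = 20 h. This is a best case, because the manual allows that the record may not yet be there at 4 hours.

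**5. Is a stop inside the PHQ9 part plausible?**

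The pre-assessment instruction is "Split into 2 calls, 1 hour each; schedule 2 days as close together as possible". Inputs for the first call: 60 min; two recordings of at least 5.5 min each; a survey part of 30 to 40 min.

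- After recordings: 60 − 2 × 5.5 = 49 min.
- Left for everything else: 49 − 40 = 9 min to 49 − 30 = 19 min.

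Orientation, video set-up, instructions, the Zoom restart and the Qualtrics check must fit into those 9 to 19 minutes, so over-running is foreseeable. This covers the PHQ9 part at pre-assessment only. The ATQ part has its own planned call. The post-assessment is headed 1.5 hours, although two one-hour sessions are scheduled.

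**6. Who is exposed**

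Only a mother who stops inside a part, after the item and before final submit. At the planned break between parts, PHQ9 #9 has already been read. The documents give neither the items' positions nor the frequency of such stops, so no number follows. If the items come late in a part, exposure is small.

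**The case against.** Four arguments on the other side have weight.

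- **The word submitted is ambiguous.** The stop-sign step ties the safety check to submission, and the 4-hour step uses the same word for the partial record. A coach could conclude that the check is due at 4 hours. The numbered steps point the other way: the reads follow the mother's final submit, and the sub-steps under the 4-hour check list only her ID and the stored record. Some ambiguity remains, and it is itself a reason to add a line.
- **The partial record may not show the items.** The manual calls them embedded data and shows them on a page after the stop sign, which a mother who stops early has not reached. This stands. The documents do not establish that a visible endorsement lies in a record staff have opened, and the 20-hour gain depends on it.
- **Exposure is narrow and unquantified.** This also stands.
- **Prompts and supports exist.** The ASRI is completed after the calls, the coach stays on Zoom throughout, and crisis numbers are loaded on the phone. These reduce the risk but direct no read.

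A reader might also infer three stronger claims that the documents do not support. One is that the item is never read if she does not resume: the manual is silent, but nothing forbids a coach from looking. Another is a 48-hour delay, from the Wednesday-and-Friday scheduling example in the Consent Call section: the specific rule for an unfinished part is the next day. The third is a breach of the 24-hour deadline on the ASRI: that duty applies once a risk has been identified.

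**Conclusion.** The gap is real, limited, and worth closing. The unfinished-survey steps at both remote assessments omit any direction to read the self-harm items; the first directed read follows final submission, and a mother who does not resume has no directed read. The documented delay is about one day, assuming calls at the same hour. It could fall to about 4 hours at best, provided partial records show the items. The number of mothers affected cannot be derived. The point does not extend to the home procedure, where the assessor is present and looks at flagged items when the iPad is handed back.

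**What to change.** In items 6d and 5d of Part VI:

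1. **Test first** whether a partial Qualtrics record shows the phq #9 and ATQ6 responses.
2. **If it does,** add one line at the 4-hour check and one at the restart log-in: read both responses. If PHQ9 #9 is 1 to 3 or ATQ6 is 3 to 5, contact the mother the same day using the decision tree and complete an ASRI. If she cannot be reached, notify the clinical supervisor the same day.
3. **If it does not,** use the stopping point already marked on the survey PDF. If the item's page was passed, make a brief private safety check before ending the call, using the decision tree's own question about thoughts of self-harm. If she is not alone, arrange a private call that day. Leave the questionnaire response unaltered.

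The cost is two added lines in each procedure, one test, a few minutes of coach time per unfinished part and an occasional same-day call. In the fallback only, self-harm is raised before the part is finished. No outcome definition or analysis changes.
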